 - iii. Modified Finnegan Evaluation (Scoring) to be done per standard of care at each institution since they are all similar and have been in place for many years. Each site involved in this study has established guidelines for starting, advancing and weaning treatment for NAS (see attached guidelines for each site). All the data regarding the treatment for NAS will be collected for the study.

2. Neonates Admitted to the NICU after Birth:

- a. ECG, Vital Signs, and Pulse Oximetry: the neonate will be stabilized after birth and then will receive a screening 12-lead ECG to rule out QTc Bazett greater than or equal to 480ms. Once the neonate is medically stable and a normal QTc confirmed by the treating physician, the neonate will receive the same study drug (ondansetron or placebo) as his or her mother; this first dose of study drug is to be given between 4-8 hours after delivery. A repeat 12-lead ECG will be done on all neonates following each of the 5 doses of study drug, between 2-5 hours after each dose of study drug. Any neonate that shows significant ECG changes will be excluded from further dosing of study medication but will continue safety follow-up
- b. Standard of Care for the NICU:
 - i. Blood pressure is measured at least once per shift. Depending on acuity and access, blood pressure will be monitored either continuously (if indwelling line is indicated for clinical care) or every 4-8 hours using non-invasive oscillometry.
 - ii. Continuous ECG, heart rate, respiratory rate and oxygen saturation monitoring are done on all NICU patients; the HR, RR, and oxygen saturations are documented in the medical record every 1-4 hours as per standard of care, with vitals documented more frequently in acutely ill infants.
 - iii. A member of the study team will visit the NICU at least once per day to ensure the neonate is doing well and that everyone on the clinical team understands the protocol and knows how to contact the principal investigator to answer questions as needed.
 - iv. Modified Finnegan Evaluation (Scoring) to be done per standard of care at each institution since they are all similar and have been in place for many years. Each site involved in this study has established guidelines for starting, advancing and weaning treatment for NAS (see attached guidelines for each site). All the data regarding the treatment for NAS will be collected for the study.

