6. Follow-up calls/visits: a research team member will call the mother of the baby once they have been discharged home, if the baby is discharged prior to Day 15 of their life. We want to follow up on the babies and learn how they are doing and make sure they are not going into "Delayed" NAS. For babies who are discharged early it is more likely they could go into delayed NAS and that is why we plan to call the mothers daily, for up to 10 days after the baby takes their last dose of study medication, to ask about their baby's status. We are interested in how the baby is feeding, are they breast or bottle feeding the baby, what is the baby's mood (crying excessively, fussy, agitated), sleeps for how many hours after feeding, sneezing a lot, sweating, vomiting, gaining weight, loose stools or watery stools, etc. We also need to ask the mother all the medications she is taking, if she is breastfeeding her baby, since we know these medications will enter the baby's system through the breast milk. If a baby is not discharged before day 15 of their life, the research team member will visit the baby in the hospital daily, for 10 days after their last dose of study drug, to check on the status of the baby from the clinical team caring for the baby. If the mother is home while the baby remains hospitalized, the research team member will also call the mother on a daily basis to maintain contact and to ask the mother all the medications she is taking if she is breastfeeding her baby (we know these medications may enter the baby's system through the breast milk).

7. The final follow-up call (or visit if the baby is still in the hospital) will occur approximately 30 days after the baby's last dose of study medication; this call (or visit) will be to determine if any previously reported adverse events have resolved and/or if any new adverse events have occurred since the last follow-up call or visit.

The primary endpoint will be the incidence of NAS in enrolled neonates and will be measured by the need for pharmacologic treatment for the symptoms of NAS (Morphine). The secondary endpoint of the severity of NAS will be measured by the length of the hospitalization (birth to discharge), the total dose of narcotic required to treat the symptoms of NAS, and the need to include barbiturates in the treatment of symptoms of NAS.

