4.3 Neonatal data

1. Gestational age, 2. Mode of delivery, 3. Birth weight, 4. Birth Length (height), 5. Neonatal co-morbidities, 6. Duration of hospital stay (birth to discharge), 7. Need for medical treatment of NAS, 8. Time from birth to initial pharmacological treatment of NAS, 9. Need for barbiturate treatment for NAS, 10. Duration of medical treatment of NAS, 11. Weight change during hospitalization, 12. Gender, 13. Modified Finnegan scores, 14. All 12-lead ECG results, 15. Frequency and duration of breast/bottle feeding in hospital and home after discharge, 16. Apgar 1min, Apgar 5 min 17. All medications used to treat NAS (drug name, dosage, route, reason for dosing, time & date), 18. pharmacokinetic blood results for ondansetron, 19. Date of birth, 20. Medical record number.

Data Security

Study team members at all sites will have access to the identifiable protected health information (PHI) of participants. During the data-collection phase of this study, all identifiable data will be kept in a locked environment. All electronic data will be encrypted and kept on a password-protected computer. A REDCap database will be designed and maintained by the study team for the compilation of all study data. This database meets all regulatory standards for safe and confidential storage and management of human subject research data. At the earliest possible time, after complete analysis and confirmation of accuracy of the data collected, all data will be de-identified.

A unique study number will be assigned to each participant. The code to link this number to PHI will be encrypted and kept in a password-protected computer. Tissue specimens for ondansetron levels will be labeled with this coded study number only and will not include any information that would link the sample to the participant. The urine toxicology screens will be analyzed in the respective hospital laboratories.

Due to the sensitive nature of the data collected and to protect the rights of the study participants, a Certificate of Confidentiality was obtained from the NIH on August 21, 2013.

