5.0 Potential Risks

Potential Risks
Ondansetron

Potential Risks	
To Mother	Well-studied in adults and considered safe Routinely given to pregnant women in first trimester for hyperemesis gravidarum and during labor as antiemetic Routine doses used in this protocol minimize risks to the mother
To Fetus	Classified as pregnancy class B (not shown to cause teratogenicity in animal studies and not well-studied in humans) Commonly used clinically in labor and delivery to treat maternal nausea, thus exposing the fetus transplacentally Considered to have minimal risk to the fetus
To Neonate	Not well-studied in this age group Used clinically to treat postoperative nausea in infants and young children and considered to carry minimal risk One double-blinded, randomized, controlled trial compared ondansetron to placebo for preventing postoperative emesis in 1-24 month olds (#22). No differences were found in number or pattern of adverse events between groups
Delayed onset of NAS	
To Mother	Not applicable
To Fetus	Onset of NAS symptoms may be delayed as a result of ondansetron treatment Given the prolonged effects of methadone, the late-onset risk may be particularly relevant to patients on methadone
To Neonate	If neonates do not demonstrate symptoms of NAS prior to discharge from the hospital; parents will be instructed to closely observe for symptoms when home and told to either call their baby's doctor or take their baby to their pediatrician if the baby is showing signs of NAS
Phlebotomy	
To Mother	Minimal risk Approximately 5 cc (one teaspoon) maximum of blood will be drawn from the mother by needle stick or she can have a finger stick if the site uses the filter paper to obtain dried blood spots. Rare side effect is hematoma and/or infection
To Fetus	Not applicable
To Neonate	Study drug will be administered to the neonate either orally or via standardized intravenous infusion (IV) technique for this population, posing no additional risk
Heel Stick	
To Mother	Not applicable
To Fetus	Not applicable
To Neonate	Do heel stick to collect 1-3 drops of blood at least twice after delivery only if blood not collected for clinical reasons in the first 12 hours after birth Minimal risk of hematoma or infection
Electrocardiogram	

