To Neonate Risk is no greater than placebo risk To minimize risk, screen for QT prolongation and give dose (determined in Aim 1) to reach blood level predicted to have desired clinical effect Dose will be within dose limits studied in slightly older infants (less than 0.15 mg/hr in 12hours) Duration of exposure will be minimized by stopping study drug after a maximum of five days of study drug treatment, Will be discontinued if related adverse events occur If QTc interval abnormalities occur or a neonate has QTcB greater than or equal to 480 ms, the neonate's study drug will be stopped and no further dosing will occur; follow up 'safety' EKGs will be done until the QTc has returned to 479ms or less, if possible. All neonates will have a screening ECG prior to their first dose of study medication & an ECG after each dose for a maximum of 6 ECGs in 5 days.
Delayed onset of NAS
To Mother Not applicable
To Fetus Risk will be managed by educating the parents about the NAS symptoms Provide parents with contact information for both their clinical caregivers and the research team Ask parents to report delayed onset to both groups Appropriate medical care will be provided Parents may receive a maximum of 10 daily follow-up telephone calls if the baby is discharged before Day 15 of life; the calls are being done to review continuation or recurrence of NAS symptoms and the occurrence of other adverse events. The research staff will call daily, through a maximum of 10 days after the last dose of study drug. If the baby is still in the hospital through Day 15 of life, this information will be gathered by the research staff visiting the neonate in the hospital. The final follow-up phone call to the parents will occur approximately 30 days after the baby's last dose of study medication to check for any occurrence of new adverse events and to inquire about the resolution of any previously reported adverse events.
To Neonate Not applicable
Phlebotomy
To Mother Minimize risks of hematoma and infection by following all hospital guidelines including using aseptic technique and applying pressure to site after sample collection Only qualified personnel may collect blood samples for analysis
To Fetus Not applicable

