7.0 Potential Benefits of the Proposed Research to the Subjects and Others

Mother-infant pairs randomized to the ondansetron arm may benefit from the following: decreased need for medical intervention for the neonate, decreased amounts of post-natal narcotic given to the neonate, decreased neonatal weight loss, and decreased length of neonatal hospital stay. There is no direct benefit to mother-infant pairs randomized to placebo. However, physician interest in mothers and neonates with narcotic exposure may make this population of women feel better understood and better cared for by the medical community. This may improve the patient's satisfaction with her care.

Because of ondansetron's safety record, the severe nature of NAS, and the significant animal and human pre-clinical data suggesting that ondansetron reduces or abolishes opioid withdrawal, we believe that the benefits of this trial far outweigh the risks.

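### Length of stay stops at first discharge and counts no readmission days, so NAS that ondansetron only postpones would appear as a shorter stay

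*Protocol*

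**What the plan says.** Length of stay is one of three secondary measures of NAS severity, beside total narcotic dose and need for barbiturates. The endpoint paragraph of protocol section 2.1.1 states that "the severity of NAS will be measured by the length of the hospitalization (birth to discharge". Section 4.3 lists the matching data item as "Duration of hospital stay (birth to discharge". That list holds one duration, with no readmission date and no count of readmission days. The SAP assigns the two-sided Wilcoxon rank-sum test at 0.05 to the continuous secondary outcomes and does not define the variable.

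Three other statements bear on this:

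- Section 5.0, on delayed NAS: "Onset of NAS symptoms may be delayed as a result of ondansetron treatment".
- Section 2.1.1, on follow-up calls: "For babies who are discharged early it is more likely they could go into delayed NAS".
- Section 7.0 names "decreased length of neonatal hospital stay" among the possible benefits of ondansetron.

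On the capture of later NAS, section 2.1.1 says "All the data regarding the treatment for NAS will be collected for the study", section 4.3 lists "All medications used to treat NAS (drug name, dosage, route, reason for dosing, time & date", and section 6.2 says "Ask parents to report delayed onset to both groups", meaning the clinical caregivers and the research team. Mothers are called daily for up to 10 days after the last dose, with a final contact about 30 days after it. Nothing says that any of this feeds into length of stay.

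**The concern.** The protocol names postponed onset as a possible effect of the study drug, so the worry is specific to one arm and not a general worry about readmission. An infant whose symptoms are held back during dosing, who goes home and who is then readmitted for NAS contributes only the short birth stay. A comparable placebo infant treated during the birth stay contributes every day. The two may spend the same number of days in hospital, yet the comparison favours ondansetron. A drug that moved NAS in time without reducing it could then appear to deliver one of the benefits that the protocol names.

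**Working it through.** **Which discharge is meant.** Section 2.1.1 speaks of one hospitalization that begins at birth. Its follow-up paragraph uses discharge for the first time the baby goes home, and section 5.0 contrasts symptoms before discharge with observation at home afterwards. First discharge is the natural reading. No statement adds readmission days.

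**One infant (assumed dates).** Home on day 5, readmitted for NAS from day 8 to day 22. The endpoint records 5 days. Days in hospital are 5 + (22 − 8) = 19.

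**Size.** The documents give no mean, SD or power for length of stay, so there is no planned figure to reproduce. What follows is an illustration.

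From the documents: 45 infants per arm (SAP); two-sided Wilcoxon at 0.05 (SAP); 42% to 94% of exposed infants develop NAS symptoms (protocol 1.0). That range is for symptoms, not morphine treatment, and is borrowed here for the share treated. Its midpoint is (42 + 94)/2 = 68%.

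Assumed: equal share treated in both arms; untreated stay uniform on 4 to 6 days (mean 5); treated stay lognormal with mean 20 days, CV 0.5 and minimum 7; no true difference in total hospital days. A share f of treated ondansetron infants, in excess of placebo, has an untreated-length birth stay and spends the remaining days on readmission.

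Infants delayed = 45 × 0.68 × f. Apparent shortening = 0.68 × f × (20 − 5) days. Rejection is from 10,000 simulated trials per case.

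| f | Infants delayed | Shortening by formula (days) | Simulated (days) | Rejection, 68% treated | 42% treated | 94% treated |
|---|---|---|---|---|---|---|
| 0 | 0 | 0 | 0.0 | 0.050 | – | – |
| 0.02 | 0.6 | 0.20 | 0.20 | 0.048 | 0.052 | 0.050 |
| 0.05 | 1.5 | 0.51 | 0.48 | 0.059 | 0.054 | 0.063 |
| 0.10 | 3.1 | 1.02 | 1.03 | 0.089 | 0.065 | 0.121 |
| 0.20 | 6.1 | 2.04 | 2.03 | 0.194 | 0.102 | 0.334 |

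With readmission days counted, rejection is 0.043 to 0.053 in every case and the mean difference is within 0.05 day of zero. With a treated mean of 15 or 25 days at 68% treated, rejection at f = 0.20 is 0.193 to 0.200.

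**A second set of assumptions.** Untreated stay 5 days, treatment adding 13 days, 68% with NAS. Shortening is 0.68 × f × 13 = 0.88, 1.77 and 2.65 days for f = 0.10, 0.20 and 0.30. A false significant result in favour of ondansetron occurs in about 8%, 20% and 39% of trials, against 2% to 3% when all hospital days are counted. The direction is the same.

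**Why both components need the same cut-off.** Suppose readmission days stop at the last contact (about day 4 + 30 = 34) but the birth stay runs on. With a 3-day gap at home, a delayed infant is cut short when the total stay exceeds 34 − 3 = 31 days. For the assumed lognormal, σ² = ln 1.25 = 0.223, σ = 0.472 and μ = ln 20 − 0.112 = 2.884. Then z = (ln 31 − 2.884)/0.472 = 1.16, an upper tail of about 12%. The loss falls only on delayed infants, so it leaves some of the same distortion. With one cut-off for both components, each such infant loses at most the 3-day gap relative to an undelayed one: at most 0.68 × 0.20 × 0.12 × 3 = 0.05 day at f = 0.20.

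**The case against.** Birth-stay length is an objective and legitimate endpoint, and the plan does not ignore delayed NAS: it provides calls, parent reports, a final contact, reporting of serious adverse events and review by the monitoring board. Bias needs an arm-specific excess of infants who are both delayed past discharge and readmitted. A delay that ends before discharge causes none. The protocol says only that onset may be delayed, and marked inflation needs about one in five treated ondansetron infants to be affected. All of that stands, and it limits the size. But none of those safeguards enters the length-of-stay comparison.

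Three stronger readings are tempting, and the documents do not support them:

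- A reader might infer that the endpoint is ambiguous between first and final discharge. The wording never says which, but the protocol's own use of discharge points to first going home.
- A reader might infer that the primary endpoint is distorted in the same way. Neither need for morphine nor total narcotic dose is limited to the birth stay, and treatment is recorded with dates, so a case treated later can still count. A shorter stay without less treatment would then show as a discrepancy.
- A reader might infer that any shorter stay in this trial is an artefact. The documents contain no delayed-NAS or readmission data from which to say so.

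**Conclusion.** The concern holds for length of stay only. As defined, the measure cannot tell NAS that was prevented from NAS that was postponed past first discharge, and the protocol itself gives a reason to expect postponement in one arm. The direction follows from the definition. The size does not: it rests wholly on assumed stays, share treated and excess delayed. Under the main assumptions the effect on the test is close to nil at an excess of 5% or less (rejection about 6% at 68% treated). It is moderate at 10% (about 1 day, 9%) and material at 20% (about 2 days, 19%, with 10% to 33% if 42% to 94% are treated). This is a secondary endpoint, so the point qualifies any claim of a shorter stay and does not threaten the primary analysis.

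**What to change.** 1. State in one sentence that length of stay runs from birth to first discharge home, and keep it as the pre-specified secondary endpoint.
2. Add a sensitivity analysis, with the same Wilcoxon test, of total hospital days: birth stay plus NAS readmission days. Count both components to the same fixed day of life in both arms. The SAP is dated March 30, 2022 and written in the past tense, so the analysis is probably post hoc. Label it so if the data are already unblinded.
3. Tabulate NAS readmissions and post-discharge NAS treatment by arm, from the follow-up calls, dated medication records and serious adverse event reports.
4. If the two measures differ in direction, or materially in size, describe any shorter first stay as possibly reflecting postponed NAS. The added analysis informs the interpretation. It is not a formal veto on the pre-specified result.

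The cost is one sentence, one analysis and one table. The real limit is data: with no readmission item in section 4.3, readmission days may have to be pieced together, and those at other hospitals may be missing. If half of the delayed infants' readmissions were missed at a 20% excess, the remaining distortion would equal the 10% case, about 1.0 day and 9% rejection. The report should therefore say how completely readmissions were ascertained in each arm.

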2.1.2 Inclusion/Exclusion

Criteria

Subjects	Inclusion Criteria	Exclusion Criteria
Maternal/Paternal	Women of reproductive age (18-45 years old, inclusive) and their fetuses/neonates. Daily opioid use for at least 3 weeks prior to delivery Gestational age of \geq 37 weeks to < 42 weeks at delivery. Competent mother willing to sign the informed consent for herself and both parents competent and willing to sign consent/permission for their neonate.	Any condition that, in the opinion of the investigator, would compromise the health of the participant (both mother and fetus) or the integrity of the data. Known allergy to the study medication. Screening 12-lead ECG, if done, showing prolonged QTc will stop the mother from receiving any study drug but her neonate can still be included in the study. Maternal ingestion or administration of ondansetron within 24 hours prior to delivery, for reasons other than study purposes, will exclude the mother and neonate.
Neonatal	Participating mother Maternal (and paternal if	QTcB greater than or equal to 480ms on any 12-lead

	present and competent) consent	ECG post delivery will stop the dosing of the study drug, but safety follow up will be done including blood samples & 12-lead ECG(s) if the mother or baby received at least one dose of study drug.
--	-----------------------------------	---

This study will include special classes of participants: pregnant women and their newborns. The focus of this study is specific to these sensitive populations of pregnant women and neonates and as such warrants their inclusion. We feel that, in balance, the potential for significant benefit to the neonatal population in this study and in future patients outweighs the risks (section 5.0 *Potential Risks* below).

4.0 Sources of Materials

4.1 Maternal and Neonatal Tissue

Maternal Tissue: one maternal blood sample for ondansetron levels will be collected within 30 minutes of delivery (pre- or post-delivery) but as close to time of birth as possible. Time of this blood sample will be recorded as accurately as possible and related to the time of birth. A maternal urine sample will be obtained prior to delivery for a toxicology screen to determine possible polysubstance abuse.

Neonatal tissue: umbilical cord blood (venous) will be collected at delivery and evaluated for ondansetron and metabolite concentrations. Between one and nine 0.1 mL blood samples (1-3drops) will be collected from the neonate to measure ondansetron and metabolite concentrations after birth. Most of these samples will be collected during clinically indicated

blood sampling to prevent additional trauma to the infant. (See Section 2.1.1. under section C. Study Procedures, #4, for details on blood draws)

